# 7.1.3 Time of Dose Resumption

Subjects who meet any of the dose suspension and dose resumption/reduction criteria specified in Table 7.1.2.1-1 and Table 7.1.2.2-1 may resume administration with the unchanged or reduced dose during the study period.

# 7.2 Volume of Blood Collected During the Study Period

The volume of blood collected at each time point during the study period (standard) is shown in Table 7.2-1. Total volume of blood collected by each subject will be approximately 80 mL.

Itom	Number of blood	Volume of blood per	Total volume of blood	
Itelli	collections	collection (mL)	collected (mL)	
Laboratory tests	10	Approximately 8	Approximately 80	
Total	10	Approximately 8	Approximately 80	

Table 7.2-1 Volume of Blood Collected During the Study Period

# 7.3 Restrictions

# 7.3.1 Physical Activity

Subjects will be prohibited from engaging in excessive physical activity, especially excessive exercise (including excessive rehabilitation, gymnastics class, and motor function evaluation in clinical research or a trial that may affect the efficacy evaluations in the study), during 7 days before the physical function evaluations specified for the study period (screening evaluation, baseline evaluation, Week 12 evaluation, and Week 24 evaluation). In addition, subjects will avoid continuous excessive exercise beyond daily activities whenever possible, stay rested and calm, and sleep sufficient hours during the study period. Study staff will instruct the subjects on appropriate levels for these daily physical activities.

# 7.3.2 Fasting

Subjects will be kept at rest and fasted for 3 to 4 hours (standard) before blood collection for laboratory tests whenever possible.

# 7.3.3 Foods and Beverages

Subjects will be prohibited from taking the following from 7 days before the start of the investigational product administration to the end of the follow-up test:

Foods and beverages containing grapefruit or St. John's Wort (including supplements)

# 7.4 Concomitant Medication/Therapy

# 7.4.1 Prohibited Concomitant Medications/Therapies

The concomitant medications/therapies specified below will be prohibited during the study period. The rationale is described in Section 14.6.

- Immunosuppressive medications (other than corticosteroids for DMD treatment)
- Persistent use of COX-1 and COX-2 inhibitors (excluding acetaminophen or other drugs that primarily centrally inhibit COX-3) and NSAIDs (temporary use for as-needed or other purpose is permissible)
- Other investigational product/therapy under study (medical device under development, etc.)
- Persistent use of mechanical ventilation (excluding non-persistent use or use while sleeping)

- Use of walking aids other than plantar orthosis (ankle foot orthosis, knee ankle foot orthosis, walker, etc.) in the 6MWD test and other motor function evaluations (use of wheelchair in daily activities is permissible)
- Rehabilitation proposed as a new program that obviously affects the present study (general or daily rehabilitation is permissible)
- Medications continuously used obviously for the improvement of the deterioration of physical function
- Sedatives used for skeletal muscle CT

The following concomitant medications (including temporary use for as-needed or other purpose) or therapies will be completely prohibited during 7 days before the motor function test:

- COX-1 and COX-2 inhibitors and NSAIDs
- Motor function test in another clinical research or trial

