# Table 1 Clinical Assessment Schedule

- 1. Permissible range for clinical assessments: After Day 1 (except for the follow-up and discontinuation tests), clinical assessments will be performed as specified in Section 5.1.10. The permissible range for the 2nd (Week 12) and 3rd hospitalization (Week 24) will be the standard hospitalization day ± 7 days. For hospitalization on any day other than the standard hospitalization day, pooled urine will also be started on the day after hospitalization, and the efficacy evaluation including that of motor function (hereinafter referred to as the efficacy evaluation), will be performed on the end day of pooled urine. However, if the efficacy evaluation cannot be performed on the end day of pooled urine to an adverse event or any other reason, the efficacy evaluation may be performed within the end day of pooled urine + 2 days (this permissible range for the efficacy evaluation will also apply to the baseline evaluation). The increase in the number of hospitalization day at ue to the delay of the efficacy evaluation (excluding prolonged hospitalization due to inpatient treatment) will not be assessed as a serious adverse event. For hospitalization within the permissible range of standard hospitalization day at Week 24 (Day 167) ± 7 days (Day 160 to Day 174), the investigational product will not be administered after the efficacy evaluation.
- 2. Subject ID code entry: A unique subject ID code will be provided to each patient whose legal representative has received an explanation of informed consent (the patient should also receive an explanation of informed consent/assent whenever possible).
- 3. Body weight: No dose increase/decrease will be considered according to body weight increase/decrease during the study.
- 4. Hospitalization: In principle, the duration of the initial hospitalization (Day -2 to Day 6) will be 8 days and 7 nights. In principle, the discharge day for the 2nd hospitalization (hospitalized on Day 83 and discharged on Day 85) and the 3rd hospitalization (hospitalized on Day 167 and discharged on Day 169) will be the day of the efficacy evaluation; however, subjects who visit the site from afar may be discharged on the day after the efficacy evaluation. Subjects will be appropriately instructed before hospitalization to bring all the prescribed investigational products (managed by their legal representatives) and subject medication diary at each hospitalization.

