- 9. Urinary tetranor-PGDM and tetranor-PGEM concentrations, urinary creatinine and creatine concentrations, urine weight, and urine specific gravity: During the baseline and administration periods, urine will be pooled (under refrigeration) for approximately 24 hours from immediately after waking on Day 4 to immediately after waking on Day 5 (initiation of pooled urine within Day 4±1 day is permissible as shown in Section 5.1.10). For urinary tetranor-PGDM and tetranor-PGEM concentrations, frozen samples will be collected by an external contractor and analyzed at the Pharmacokinetics Research Laboratories of Taiho Pharmaceutical Co., Ltd. Urinary creatinine and creatine concentrations, urine weight, and urine specific gravity will be measured at the study site. Urine volume (mL) will be calculated from the measured urine weight (g) and urine specific gravity (g/mL) at the study site.
- 10. Subject medication diary: The subject and his legal representative will bring the subject medication diary at each visit and submit it during the medical examination. The subject medication diary will be collected at each visit for ongoing drug accountability check and appropriate instruction. If the subject medication diary is left behind at home, it may be collected at the subsequent visit. Drug accountability to facilitate additional prescription of the investigational product is described in Note 5, above.
- 11. Assessments of concomitant medication/therapy and adverse events: Investigated from the time of informed consent to the end of the follow-up period (follow-up or discontinuation test)
- 12. Data from any evaluation/test performed as specified within 14 days before enrollment can be used as screening data, even if obtained before informed consent.
- 13. Initial hospitalization: The subject will be hospitalized (on Day -2) within 12 days after enrollment.

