- 14. Administration start day (Day 1): The administration of the investigational product will be started after dinner on the end day of pooled urine (within 14 days after enrollment); however, if it is not possible to perform the efficacy evaluation (corresponding to Note 1) due to an adverse event or any other reason, or to start the investigational product administration on the end day of pooled urine, the administration may be started after dinner within the end day of pooled urine + 2 days (within up to 16 days after enrollment) (the actual administration start day will be designated as Day 1). The increase in the number of hospitalization days due to the delay of the administration start day (excluding prolonged hospitalization due to inpatient treatment) will not be assessed as a serious adverse event.
- 15. Clinical assessments in the baseline period: Performed no later than administration on the investigational product administration start day (administration after dinner on Day 1), in principle
- 16. Discontinuation test: Performed at the first visit after discontinuation whenever possible (safety endpoints will be evaluated)
- 17. Efficacy endpoints on the end day of administration: Evaluated after the last dose of the investigational product (standard: administration after breakfast on Day 169)
- 18. Follow-up test: Performed 21 days after the last day of the investigational product administration (standard day ± 7 days is permissible).
- 19. Endocrinology at the follow-up test: Performed only if an abnormal change (adverse event) is observed in the test on the discharge day for the 3rd hospitalization (standard: Day 169). Such an endocrinological test will be performed around 8:00 to 10:00 am on the follow-up test day. For subjects who visit the study site from afar, a stay at night before the follow-up test day (stay at or outside the study site; planned hospitalization or stay at a nearby facility) will be considered to collect blood within the specified time window whenever possible.

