#### 8.2 Urine Sampling

Time points of pooled urine for measurement of individual concentrations and other parameters for pharmacodynamic and exploratory endpoints will be as follows:

- From immediately after waking on the day after initial hospitalization to immediately after waking on the efficacy evaluation day at baseline (the day after start of pooled urine);
- From immediately after waking on Day 4 to immediately after waking on Day 5;
- From immediately after waking on the day after the 2nd hospitalization to immediately after waking on the efficacy evaluation day (Week 12 evaluation); and
- From immediately after waking on the day after the 3rd hospitalization to immediately after waking on the efficacy evaluation day (Week 24 evaluation).

The urine samples will be stored under refrigeration (approximately 4°C) during pooled urine. At each time point of pooled urine described above, parts of the urine will be transferred to urine containers (approximately 4-mL each) and stored frozen (at or below approximately -70°C) at the study site as samples for urine tetranor-PGDM/-PGEM concentration measurement. The frozen samples will then be collected by an externally contracted carrier and analyzed at the Pharmacokinetics Research Laboratories of Taiho Pharmaceutical Co., Ltd.

In addition, at each time point of pooled urine described above, the urine volume (mL) will be calculated from the separately measured urine weight (g) and urine specific gravity (g/mL), and approximately 4-mL each of the urine collected in 2 containers as samples for urine creatinine and creatine concentration measurement at the study site. Urine creatinine and creatine concentrations will be measured at the study site.

For details regarding the collection and treatment of samples for urine tetranor-PGDM/-PGEM concentration measurement, the separately prepared "Procedures for Treatment of Samples for Urine Tetranor-PGDM/-PGEM Concentration Measurement" will be followed.

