#### 14.3 Rationale for the Inclusion Criteria

- (1) This criterion was set to ensure ethical conduct of the study in accordance with GCP and the principles of the Declaration of Helsinki by including only subjects from whom informed consent can be obtained in an appropriate manner through their legal guardians (legal representatives).
- (2) This criterion was set to identify patients with DMD or with symptoms characteristic of DMD to ensure appropriate evaluation of the study.
- (3) Age 5 was set as the minimum age for inclusion because this is considered the minimum age at which specified study procedures can be performed and a definitive diagnosis of DMD can be made. In addition, only male pediatric patients will be included in this study on the grounds that DMD is usually seen in boys, although no nonclinical study of fertility and early embryonic development has been conducted.
- (4) The lower and upper limits of body weight were set based on an expected body weight distribution of the ambulatory patients with DMD.
- (5) This criterion was set to select patients who can complete individual motor function evaluations of the efficacy endpoints.
- (6) This criterion was set to select patients who can stay in the hospital during the hospitalization period specified in the study, because approximately 24-hr (1 day) pooled urine is required a total of 4 times during the study period (baseline period, Day 4, Week 12, and Week 24).
- (7) This criterion was set to ensure proper conduct of the study in consideration of the formulation of the investigational product.
- (8) The only currently available drug therapy for DMD is treatment with Predonine® Tablets 5 mg (a synthetic corticosteroid), for which approval has been only obtained for additional indication in September 2013 following its public knowledge-based application in February in the same year, and rehabilitation and management of concurrent illnesses, etc., remain the mainstays of treatment. Under ethical considerations in view of the scarcity of drug therapy options, the concomitant use of steroids will be allowed in patients who are on corticosteroids at the time of informed consent as far as no changes are made to their dosage regimen after informed consent.

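### The complete COX-inhibitor/NSAID ban lapses after the baseline motor test, so as-needed use is allowed up to the end of the Day 4-5 pooled urine, the only one of four collections left uncovered

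*Protocol*

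**What the plan says.** Protocol 7.4.1 has two tiers for COX-1/COX-2 inhibitors and NSAIDs. Persistent use is prohibited throughout, but "temporary use for as-needed or other purpose is permissible". A stricter rule, which includes as-needed use, applies around motor testing: these drugs "will be completely prohibited during 7 days before the motor function test". Acetaminophen and similar centrally acting drugs are exempt from the ban on persistent use, and section 14.6 says that they are not prohibited.

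Section 7.3.1 lists the physical function evaluations as "screening evaluation, baseline evaluation, Week 12 evaluation, and Week 24 evaluation", and Table 1 schedules 6MWD at the same four points.

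Urine follows a different calendar. Section 14.3 explains that "approximately 24-hr (1 day) pooled urine is required a total of 4 times during the study period": at baseline, Day 4, Week 12 and Week 24. Under section 8.2, three of these run up to the morning of an efficacy evaluation day. The fourth is collected "From immediately after waking on Day 4 to immediately after waking on Day 5", and Note 9 to Table 1 adds that "initiation of pooled urine within Day 4±1 day is permissible".

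Section 14.6 justifies the drug restrictions by the efficacy and safety evaluations. It accepts that COX-1 and COX-2 inhibitors may affect the study, but it does not mention the urine measurements.

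**The concern.** Section 1.1 places cyclooxygenase upstream of prostaglandin D synthase, and section 8.4 says the pharmacodynamic analysis is meant to show reduced PGD2 production through HPGDS inhibition. A COX inhibitor taken shortly before or during a collection could lower tetranor-PGDM, and tetranor-PGEM too, without any action of TAS-205 on its target.

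The protocol protects the pharmacodynamic reading elsewhere. Section 14.4 excludes certain allergic and inflammatory conditions on that ground, and section 14.8 gives the urine measurements as one reason for fixing concomitant medication. The NSAID rule is tied to motor tests alone, so a urine collection with no motor test after it is unprotected.

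At stake is the first pharmacodynamic reading of a high dose that, according to section 1.3.2, has not been given in clinical studies. Day 4-5 values feed the summaries and two-sample t-tests at each time point in SAP 6.3, the one-sample t-tests against a 0% change rate in SAP 6.6, and any SAP 6.3 correlation that uses the Day 4 change rate. The one-sample tests have no comparator, so NSAID use that was equal across arms would not cancel out of them.

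**Working it through.** The documents state no figure for this gap. It follows from the calendar.

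**Inputs**

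- Day numbering: Note 4 to Table 1 says "the duration of the initial hospitalization (Day -2 to Day 6) will be 8 days and 7 nights". Eight days from Day -2 to Day 6 means that there is no Day 0.
- Baseline motor test: done on the end day of the baseline urine, or up to 2 days later (Note 1), and in principle no later than the first dose on Day 1 (Note 15).
- Delayed dosing: Note 14 says "the administration may be started after dinner within the end day of pooled urine + 2 days". Day 1 is the actual dosing day.
- Second urine: starts on Day *s* = 3, 4 or 5 and ends one day later.

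**Length of the uncovered window**

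Let *D* be the days from the baseline motor test to the first dose (0 to 2). The second urine ends on Day *s* + 1, which is *s* days after Day 1, so the window is *D* + *s*.

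- Standard schedule: 0 + 4 = 4 days.
- Urine tolerance only: 0 + 3 = 3 to 0 + 5 = 5 days.
- Motor test on time and dosing 2 days late: 2 + 3 = 5 to 2 + 5 = 7 days.

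Seven days needs three things together: an on-time motor test, dosing delayed by 2 days, and a urine started a day late. If the motor test slips with the dosing, *D* = 0 and the window stays at 3 to 5.

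**Coverage of each collection**

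| Collection | Motor test that follows | Inside the 7-day ban? |
|---|---|---|
| Baseline | 0 to 2 days after it ends | Yes |
| Day 4-5 | Week 12 | No |
| Week 12 | 0 to 2 days after it ends | Yes |
| Week 24 | 0 to 2 days after it ends | Yes |

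For the three covered collections, the 24-hour urine starts 1 to 3 days before the test. The ban is then already 7 - 3 = 4 to 7 - 1 = 6 days old. For Day 4-5, the next ban starts on Day 85 - 7 = Day 78. The range is Day 78 - 7 = 71, for admission on Day 76, to Day 94 - 7 = 87, for admission on Day 90 with a 2-day delay. So 1 of 4 collections, or 1 of 3 after dosing, is uncovered.

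**Illustration of size (assumed inputs)**

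The documents give neither the frequency of as-needed use nor its effect on tetranor-PGDM. Suppose one user among 11 subjects and a fall of 50% to 80% in that subject.

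- Placebo arm mean change rate: 50/11 = 4.5 to 80/11 = 7.3 percentage points downward.
- Active arm, if TAS-205 has already lowered the value by 30% to 50%: 0.5 × 50/11 = 2.3 to 0.7 × 80/11 = 5.1 points downward.

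With no users, the shift is zero.

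**The case against.** Day 4-5 is peripheral. The exploratory objective in section 2.3 concerns 24 weeks of dosing, and two fully covered urines follow. The correlations and covariance models with tetranor-PGDM in SAP 6.6 use Day 168. Exposure is also constrained: persistent use is banned, the ban before the baseline test limits carry-over, the boys are inpatients, acetaminophen is available, and section 5.1.11 records every drug. Data of doubtful status can be discussed with the medical expert before code breaking. Phase I suggested no TAS-205 effect on tetranor-PGEM, so a joint fall in both metabolites could flag NSAID use. Blinding and randomisation make occasional use mainly noise between arms. The permission may also be deliberate, since section 14.6 discusses the arachidonic acid cascade and as-needed use is still allowed.

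Most of this stands and keeps the point small. It does not close the gap. Inpatient status and drug recording help detect use but do not forbid it. The general routes for abnormal or questionable data do not say whether urine collected under a permitted NSAID counts. If the permission is deliberate, section 14.6 does not explain it for this collection.

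A reader might infer that the gap distorts the relation between PGDM and motor function. The documents do not support that. Table 1 has no motor, CT or strength measure between Day 1 and Week 12; only lung function, body composition and CK are measured near that time, on Day 6.

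It can also be argued that a sensitivity analysis alone would be enough. It would show the effect of recorded use, but it would not prevent that use, and with 11 per arm each omitted sample costs information.

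**Conclusion.** The gap is real and minor. As-needed COX-1/COX-2 inhibitors and NSAIDs are permitted from after the baseline motor test to the end of the Day 4-5 urine: 4 days on the standard schedule, 3 to 5 with the urine tolerance, and up to 7 only in the compound case above. No other clause in the documents covers that collection.

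The consequence is confined to the exploratory Day 4-5 pharmacodynamic results. Its size is unknown and may be zero; the illustrated shifts rest wholly on assumed frequency and effect. I do not count the mixed model, because it is unclear whether Day 4 enters it: the SAP code notes list only Weeks 12 and 24.

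A reader might infer that the primary 6MWD comparison or the later PGDM results are compromised. They are not. The 7-day ban precedes each 6MWD test and covers the Week 12 and Week 24 urines. Nor does permitted use in the gap remove a subject from the PPS, since it is not use of a prohibited drug.

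**What to change.** 1. In protocol 7.4.1 and 14.6, continue the baseline complete ban through the end of the Day 4-5 collection, with acetaminophen still allowed. Leave the Week 12 and Week 24 windows as they are.
2. In Table 13.1.2-1 and SAP Table 4.1, state that a breach of this extension alone does not remove a subject from the PPS. Without that clause, a breach would count as prohibited use and take a boy out of the primary 6MWD analysis because of a urine rule.
3. In SAP 6.3 and 6.6, keep all samples in the main pharmacodynamic analysis. Add one Day 4-5 sensitivity analysis that omits the urine of any subject with recorded COX-1/COX-2 inhibitor or NSAID use between the baseline motor test and the end of that collection. The data are already collected under section 5.1.11.

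The cost is one line in each of two protocol sections, one clause in two tables, and one extra analysis. The downside for subjects is about 4 more inpatient days without NSAIDs; no outpatient days are added.

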# 7.4.2 Concomitant Medications/Therapies Requiring Precaution

The use of the concomitant medications requiring precaution specified below will be avoided whenever possible; if used, care should be taken, especially when used with the investigational product. The rationale is described in Section 14.7.

- Potent cytochrome P450 (CYP) 3A4 inhibitors including itraconazole, ketoconazole, atazanavir, indinavir, nelfinavir, ritonavir, and saquinavir
- P-glycoprotein (P-gp) inhibitors including ketoconazole, erythromycin, and diltiazem

Concomitant therapies requiring precaution will not be set.

# 7.4.3 Restricted Concomitant Medications/Therapies

The dosage regimen (dosage and administration) of the following concomitant medications will be restricted during the study period: The rationale is described in Section 14.8.

• Oral steroids for DMD treatment:

In principle, the prescription-based dosage regimen will not be changed after obtaining informed consent (This will not be applied if the dose must be reduced or suspended due to an adverse event or other reasons, nor will this be applied if change in the dosage regimen for the subject with unexpectedly marked increase in body weight associated with growth is determined to be necessary by the investigator from an ethical viewpoint. Any change in the dosage regimen shall be recorded with the detailed medical rationale/reason in the source documents.).

Restricted concomitant therapies will not be set.

